Non-inferiority unblinded randomized controlled trial where subjects will be randomized in a ratio of 1:1 to Dilapan-S[®] and misoprostol groups. We decided to use the non-inferiority design as Misoprostol is considered as one of the accepted and standard treatments for induction of labor in United States. Our assumptions for the trial are based on results of PROBAAT-II trial, a large well designed randomized trial conducted in EU for studying efficacy of mechanical and pharmacological methods for labor induction. Assuming a rate of vaginal delivery within 36 hours to be 65% for Misoprostol and 71% for mechanical method (based on data on transcervical Foley catheter in PROBAAT-II [3] and a recent trial comparing Foley catheter to Dilapan-S[®] for cervical ripening done by Saad et al. [12]), with a non-inferiority margin of 10 % and an expected screen failures rate of 5%, a total of 322 subjects will need to be randomized in ratio 1:1 to Dilapan-S[®] vs Misoprostol group. 153 eligible and assessable subjects are needed in Dilapan-S[®] group and 153 in Misoprostol group for analysis. The study is powered at 85% for detecting the primary outcome with a type 1 error at 2.5% for one-sided test.

Objective for the trial

To assess efficacy of cervical ripening with Dilapan-S[®] or Misoprostol in women undergoing induction of labor.

Primary research question (primary endpoint)

Proportion of subjects achieving vaginal delivery within 36 hours after the initiation of the cervical ripening in Misoprostol and Dilapan-S[®] group.

Rationale: The authors of PROBAAT-II study make the valid point that as an outcome of labor induction, giving birth vaginally is more important than how quickly it happens; therefore 24 hours may not be a long enough time for appropriate assessment. Indeed, the effect found in the PROBAAT-II study would have been reversed had the outcome been measured by assessing vaginal delivery within 36 hours. There is therefore a call to standardize the outcome measure in IOL trials to a vaginal delivery within 36 hours [6], particularly when mechanical methods are employed.

Secondary research questions (secondary endpoints)

- Bishop score at 12 hours after the intervention
- Percentage of subjects delivering vaginally in 24 hours after the initiation of intervention
- Overall vaginal delivery rate in each group
- Rate of operative deliveries
- Rate of cesarean deliveries in each group.
- Total length of hospital stay

Maternal outcomes:

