# 3.2. SECONDARY OUTCOMES

Individual and composite maternal and fetal outcomes including overall vaginal delivery rate, cesarean section rate, Bishop score after cervical ripening, infections, postpartum hemorrhage. Neonatal outcomes include Apgar scores, NICU admission and sepsis.

Secondary endpoints are:

- Overall vaginal delivery rate in each group
- Rate of caesarean deliveries in each group
- Rate of operative deliveries (vaginal plus caesarean)
- Bishop score at 12 hours after the intervention and change in Bishop score
- Percentage of subjects who did not receive all 6 misoprostol doses
- Percentage of subjects with failed Dilapan-S insertion
- Percentage of subjects delivering vaginally in 24 hours after the initiation of intervention

- Delivery time
- Initiation of cervical ripening to delivery time
- Initiation of oxytocin to delivery time
- Total length of hospital stay
- Maternal outcomes:
  - Chorioamnionitis
  - Endometritis within 2 weeks after delivery
  - Postpartum haemorrhage (EBL>1000cc and/or drop in HCT by 10 points)
  - 3rd and 4th degree lacerations
- Neonatal outcomes:
  - Apgar score <7 at 5 min
  - Cord arterial blood pH and Cord arterial blood pH <7
  - Cord arterial blood base excess and Cord arterial blood base excess > -12mmol/l
  - NICU admission within 2 weeks after study intervention
  - Antibiotic use within 2 weeks after study intervention

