#### 7.3. ANALYSIS OF SECONDARY ENDPOINTS

All quantitative secondary variables will be summarized separately for each arm. Means of the two treatment arms will be compared with two-sample t-test and Wilcoxon rank-sum test as appropriate.

All secondary variables involving rates and percentages, will be calculated for both arms. Difference in proportions will be derived together with a 95% two-sided confidence interval. The difference between treatment groups will be concluded if the confidence interval does not include zero.

Maternal and neonatal outcomes will be summarized as reported in the CRF.

Delivery time will be presented using Kaplan-Meier curves with censoring for caesarean delivery.

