#### Efficacy data

Table	14.2.1	Summary of Delivery Characteristics
Table	14.2.2.1	Primary analysis for proportion of Vaginal Delivery within 36 hours
Table	14.2.2.2	Analysis for proportion of Vaginal Delivery within 24 hours
Table	14.2.3.1	Analysis for proportion of Mode of Delivery
Table	14.2.3.2	Analysis of Delivery Time
Table	14.2.4.1	Analysis of Bishop score
Table	14.2.5.1	Analysis of Total Length of Hospital Stay
Table	14.2.6.1	Summary statistics of Maternal Outcomes
Table	14.2.7.1	Summary statistics of Neonatal outcomes

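### The two time-to-delivery intervals have no caesarean rule; under the SAP's default tests a caesarean counts as an ordinary delivery, so the arm comparison has no consistent clinical direction

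*SAP*

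**What the plan says.** SAP 3.2 lists three time endpoints as separate bullets: delivery time, "Initiation of cervical ripening to delivery time" and "Initiation of oxytocin to delivery time". None names a route. Another bullet in the same list does: "Percentage of subjects delivering vaginally in 24 hours after the initiation of intervention".

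SAP 7.3 sets a general rule. It begins "All quantitative secondary variables will be summarized separately for each arm" and continues "Means of the two treatment arms will be compared with two-sample t-test and Wilcoxon rank-sum test as appropriate". It gives no instruction for women delivered by caesarean. Later in 7.3 comes one sentence that does: "Delivery time will be presented using Kaplan-Meier curves with censoring for caesarean delivery". That sentence names only delivery time, describes a presentation, and attaches no test.

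The SAP's list of efficacy tables has one entry on the subject, "Analysis of Delivery Time", and no separate table for either interval.

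In the protocol, the rationale for the primary endpoint takes up the view that "giving birth vaginally is more important than how quickly it happens". The Delivery period section says that date, time and mode of delivery are collected.

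**The concern.** On the literal text, a caesarean at 10 hours is a failure on the primary endpoint but one of the best values on the interval scale. A vaginal birth at 34 hours is a primary success but a poor value. A caesarean for failed induction at about 40 hours is a failure on both.

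A difference in mean or rank between arms therefore cannot be interpreted without knowing how many caesareans each arm had and when. Either arm could be reported as significantly quicker or slower when its vaginal births take exactly as long as the other arm's.

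Section 7.3 would also hold two treatments of caesarean for closely related endpoints: an ordinary event time in the test and a censored time in the curve.

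**Working it through.** **Group size.** The documents give no figure for the time endpoints, so the only plan figure used is 153 per arm. It reproduces from the protocol's Study Design section (65% and 71%, margin 10%, one-sided 2.5%, power 85%):

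n = (1.960 + 1.036)² × (0.65×0.35 + 0.71×0.29) / (0.06 + 0.10)² = 8.978 × 0.4334 / 0.0256 = 152.0, taken up to 153.

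**Timing that the documents imply.** Under Labor Induction in the protocol, failed induction is diagnosed after 24 h of amniotomy with oxytocin, normally following the 12 h assessment. That gives 12 + 24 = 36 h or later. A caesarean for fetal or bleeding reasons could come much earlier.

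**Assumed times (not in the documents).**
- Vaginal births: mean 26 h, SD 9 h, the same in both arms.
- Late caesareans: uniform on 36-44 h, mean 40 h.
- Early caesareans: uniform on 6-14 h, mean 10 h.
- Reference arm: 72% vaginal, 25% late caesarean, 3% early caesarean.
- Other arm: extra caesareans replace vaginal births.

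**Mean shift.** Each point moved from vaginal to early caesarean changes the mean by 0.01 × (10 - 26) = -0.16 h. Each point moved to late caesarean changes it by 0.01 × (40 - 26) = +0.14 h.

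**Reference arm.** Mean = 0.72×26 + 0.25×40 + 0.03×10 = 29.02 h. Second moments are 26² + 81 = 757 (vaginal), 40² + 5.33 = 1605.3 (late) and 10² + 5.33 = 105.3 (early). Variance = 0.72×757 + 0.25×1605.3 + 0.03×105.3 - 29.02² = 107.4.

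**Probability of a significant result (two-sided 5% t-test, one direction).** Φ(|shift|/SE - 1.96), with SE = √[(107.4 + V)/153] and V the variance in the other arm.

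| Extra caesareans | Shift | V | SE | t-test, by formula | Simulation |
|---|---|---|---|---|---|
| 10 early | -1.6 h | 132.5 | 1.252 | faster, 25% | faster, about 24% (t), 18% (Wilcoxon) |
| 15 early | -2.4 h | 143.2 | 1.280 | faster, 47% | faster, about 47% (t), 37% (Wilcoxon) |
| 5 early, 5 late | -0.1 h | 123.0 | 1.227 | faster, 3% | about nominal |
| 10 in ratio 3:25 early to late | +1.1 h | 112.4 | 1.198 | slower, 15% | slower, 15% (t), 17% (Wilcoxon) |
| 10 late | +1.4 h | 109.0 | 1.189 | slower, 22% | slower, about 22-26% over both tests |

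The nominal rate in one direction is 2.5%.

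**Primary endpoint in the same scenarios.** With 10 points fewer vaginal births, the loss on vaginal delivery within 36 h is 10 × Φ((36 - 26)/9) = 10 × 0.867, about 9 points, whether the caesareans are early or late. The time comparison gives opposite answers for the same loss.

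**Other assumptions.** Take vaginal time with mean 24 h and SD 9 h in both arms, and caesarean in 20% versus 30%. Caesareans at mean 14 h shift the mean by 0.10 × (14 - 24) = -1.0 h, significantly faster in 16% (t) or 19% (Wilcoxon). At mean 24 h there is no shift and about 2%. At mean 38 h the shift is 0.10 × (38 - 24) = +1.4 h, significantly slower in 24%.

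**With caesarean as worst rank.** In these 20% versus 30% scenarios the arm with more caesareans is significantly favoured in 0.1% of trials or fewer. It is significantly worse in 32-34%, wherever the caesareans fall in time.

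**The case against.** The best defence is that the SAP never says the intervals end at delivery by any route; it is silent. The caesarean-censoring sentence in 7.3 may be meant to govern them. A Kaplan-Meier curve needs a time origin, the bare delivery-time bullet has none, and the two interval bullets supply one each. The single delivery-time table points the same way. This stands as a plausible reading, and it means that a reader who infers a deliberately chosen any-route endpoint goes further than the text. It does not remove the problem. The sentence attaches no test, so the t-test or Wilcoxon still applies by the general rule. Censoring also treats a woman delivered by caesarean as if she could still deliver vaginally, when caesarean is a competing event.

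A reader might also infer that an arm with more caesareans will tend to be declared quicker. That holds only if the excess is mainly early. No passage supports an excess of 10 to 15 points of early caesareans, and failed-induction caesareans fall late and push the other way.

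Nor does the plan contradict the protocol's rationale. The statement that vaginal birth matters more than speed justifies the choice of primary endpoint and does not bar a secondary interval. Vaginal, caesarean and operative delivery rates are reported alongside, so an excess of caesareans would be visible.

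**Conclusion.** The concern holds as a gap in definition combined with a default test that does not suit the endpoint. As written, the two intervals have no route and no caesarean rule, and the test that 7.3 assigns to them does not match the censoring that it uses for delivery time. The result can move in either direction for the same loss of vaginal births: from -1.6 h (faster in about 24% or 18% of trials) to +1.4 h (slower in about 22-26%) for 10 extra points of caesarean, and about nominal when early and late are balanced.

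These sizes rest on assumed times and caesarean shares. They show how the comparison behaves and do not predict this trial's result. The endpoints are secondary, and the trial was not sized for them. It would be wrong to infer that the non-inferiority conclusion is at risk: it uses vaginal delivery within 36 hours and is not touched.

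**What to change.** In SAP 3.2, define the event for the time endpoints as vaginal delivery. In SAP 7.3, apply one caesarean rule to all of them, replacing both the t-test or Wilcoxon on any-route times and the censoring of caesarean.

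- **Ripening to delivery:** compare all randomised women by a rank test stratified by parity and gestational age, with every caesarean given the worst rank. Cumulative incidence of vaginal delivery with caesarean as a competing event is an acceptable alternative. State the clock start for a randomised woman in whom ripening never begins.
- **Delivery-time curves:** show cumulative incidence of vaginal delivery, with caesarean as a competing event, and name the time origin.
- **Oxytocin to delivery:** give descriptive summaries by mode of delivery, without a between-arm test. The clock starts after randomisation and only in women who receive oxytocin, so the arms compared would no longer be the randomised ones.
- **Any-route times:** give descriptive summaries by mode of delivery, without a between-arm test.

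The cost is a few lines in the SAP. Time and mode of delivery are already collected. The downside is that the result is a rank or cumulative-incidence comparison and not a mean difference in hours.

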Induction of labor is one of the most common obstetric procedure [1]. Current practice in United States is to admit the patients to labor and delivery floor once a decision to proceed with induction of labor has been made. Majority of these women are candidates for cervical ripening as their cervix is found to be unfavorable for initiation of oxytocin based on the assessment of Bishop Score at the time of admission. Bishop score of 6 or more is a good predictor of likelihood of achieving vaginal delivery within 24 hours after initiation of labor induction. Cervical ripening is a process by which cervix undergoes enzymatic dissolution of collagen fibrils and changes in intercellular matrix, leading to increase in water content and softening [1]. These changes transform cervix to a soft, pliable structure that undergoes dilatation and effacement in response to uterine contractions. Two commonly methods used for cervical ripening are prostaglandins and mechanical devices.

Misoprostol

Misoprostol is a prostaglandin E1 analog approved for treatment and prevention of gastric ulcers. Misoprostol acts on the intracellular matrix of the cervix, causes breakdown of the collagen fibrils leading to cervical softening. It also induces uterine contractions. ACOG has indicated that use of Misoprostol appears to be safe and effective for induction of labor when used in low dose [2]. Despite a large number of trials of Misoprostol for cervical ripening there is no clear consensus as to the optimal oral dose, dosing interval and the maximum number of doses that can be given. In PROBAAT II, a non-inferiority trial comparing oral Misoprostol to Foley catheter for cervical ripening, Eikelder, Jozwiak et al. [3] used 50mcg of Misoprostol orally, dosed every 4 hours with a maximum of three times per day. Ibraheemi et al. [4] in their recent RCT - Misoprostol with Foley bulb compared with Misoprostol alone for cervical ripening, used 25 mcg of Misoprostol vaginally every 4 hours to a maximum 6 doses. Levine et al. [5] in their randomized clinical trial - Foley or Misoprostol for management of induction used 25 mcg of Misoprostol every 3 hours with a maximum of 6 doses over 24 hours. WHO [10] has suggested using Misoprostol 25 mcg orally every 2 hours.

COLUMBIA UNIVERSITY College of Physicians and Surgeons

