
Randomization plan will be generated based on computer program. Subjects will either undergo Dilapan-S[®] insertion or receive up to 6 oral doses of 25 mcg of Misoprostol based on their allocation to treatment groups.

Baseline procedures

Subject enrolled in the study will be evaluated by a care provider and a history and physical examination including a sterile speculum and digital vaginal exam will be done. Provider will also review maternal vital signs and indication for induction of labor. All enrolled subjects will have CTG monitoring for at least 20 minutes prior to the planned intervention and IV access and Type and Screen as per the labor and delivery standard procedure.

Pre-induction

Arm A: Dilapan-S[®] group

Patients who are randomized to receive Dilapan-S[®], will have rods of Dilapan-S[®] inserted in their cervix by the supervising provider, under aseptic precautions with a speculum exam, either digitally or using a sponge forceps, as per manufacturer's recommendations [Appendix 1]. The Bishop score at the time of eligibility assessment and number of rods inserted will be recorded. Dilapan-S[®] will be left in cervix for 12 hours (±30 minutes). Patients will be allowed to ambulate, shower and have light meals as long as they meet the criteria based on institutional guidelines for intermittent fetal heart monitoring. "Nothing per vagina" including douching and no bathing is allowed.

Arm B: Misoprostol group

For subjects randomized to Misoprostol group, after the baseline assessment and a reassuring CTG monitoring for 20 minutes, 25mcg of Misoprostol will be administered orally every 2 hours (±15 minutes) to a maximum of 6 doses. All subjects will have continuous fetal monitoring. A dose will be held if patient is noted to have uterine tachysystole, hyperstimulation, fetal heart tracing abnormalities or 3 or more painful uterine contractions over a period of 10 minutes (indicating onset of labor). Administration of Misoprostol will be done by the nurse assigned to the patient.

Subjects in both groups will remain on labor and delivery (L&D) floor and will have continuous fetal monitoring as per the institutional guidelines.

All study participants will be examined after 12 hours of receiving intervention unless there is an indication for an exam prior to this period. Reasons for an exam earlier than 12 hours after the initiation of cervical ripening intervention include:

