- 1. Onset of spontaneous labor (defined as regular painful uterine contractions with a dilation of ≥ 4 cm and effacement of 75% or more)
- 2. Vaginal bleeding
- 3. Persistent Category 2 or Category 3 fetal heart tracing
- 4. Spontaneous rupture of membranes
- 5. Spontaneous expulsion of Dilapan-S[®] rods (*if Bishop score is still <6, another set of rods may be placed and allowed to remain in situ for a maximum of 12 hours cumulative based on clinical assessment made by the supervising provider*)
- 6. AROM is indicated

Labor Induction

Subjects in both groups will have an assessment of Bishop score 12 hours after the study intervention and evaluated for amniotomy and Oxytocin infusion. Oxytocin will be initiated as per the institutional guidelines. Amniotomy will be undertaken as soon as clinically feasible. If after 24 hours of amniotomy with Oxytocin the patient is not in active labor [cervical dilatation<6 cm], a diagnosis of failed induction will be made [Appendix 2] and a decision will be made to proceed with cesarean section. During labor, decision to proceed with operative delivery or cesarean section will be made by the attending physician supervising the care of the patient. All subjects will have the option to receive epidural during labor for pain management.

COLUMBIA UNIVERSITY College of Physicians and Surgeons

Oxytocin administration CUMC:

Oxytocin will be administered for labor induction and augmentation as per the institutional guidelines [Appendix 2]. Oxytocin is supplied to L&D unit in prepared bags with 30 units of Oxytocin in 500 cc of Normal Saline. Oxytocin will be initiated at 1 milliunit/minute and increased every 15 minutes, till an optimal response is obtained.

The maximum dose is limited to 40 milliunits/minute.

UTMB:

Oxytocin will be administered for labor induction and augmentation as per the institutional guidelines [Appendix 3]. Oxytocin is supplied to L&D unit in prepared bags with 20 units of Oxytocin in 1000 cc of Lactated Ringers. Oxytocin will be initiated at 2 milliunit/minute and increased every 20 minutes, till an optimal response is obtained. The maximum dose is limited to 40 milliunits/minute.

Delivery period

Data for date, time and mode of delivery and intra-partum complications (incl. those found during induction period) will be collected. The complications will include, but are not limited to following:

- Uterine tachysystole (defined as > 5 contractions per 10 minutes averaged over 30 minutes.

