### 6. STATISTICAL PRINCIPLES

### 6.1. GENERAL STATISTICAL CONSIDERATIONS

The statistical analyses will be performed in accordance with ICH E9 guideline (ICH E9, 1998) and is based on all collected data. Statistical analyses will be performed at the 5% significance level.

The quantitative variables will be summarized using the following parameters:

- Number of non-missing data,
- Mean,
- Standard deviation,
- Median,
- Minimum and Maximum (range),
- First and Third quartiles (interquartile range).

The categorical/qualitative variables will be summarized using the following parameters:

- Number of non-missing data,
- Frequencies and percentages.

All collected data will be presented in data listings.

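### Oxytocin-to-delivery time is tested between arms although it exists only for women who start oxytocin after randomisation, so the test can show a difference when treatment has no effect on labour speed

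*SAP*

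**What the plan says.** SAP 3.2 includes "Initiation of oxytocin to delivery time" among the secondary endpoints, directly below the interval from the start of cervical ripening to delivery. The protocol's own list of secondary endpoints contains neither interval.

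SAP 7.3 states that "All quantitative secondary variables will be summarized separately for each arm" and continues: "Means of the two treatment arms will be compared with two-sample t-test and Wilcoxon rank-sum test as appropriate". The oxytocin interval is quantitative, so on a plain reading it is tested. SAP 6.1 adds "Statistical analyses will be performed at the 5% significance level". Nothing marks this comparison as descriptive.

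Oxytocin is not given to everyone at a fixed time. Under Labor Induction, the protocol has women in both arms assessed 12 hours after the intervention and "evaluated for amniotomy and Oxytocin infusion". Its list of reasons for an earlier examination begins with "Onset of spontaneous labor (defined as regular painful uterine contractions". Of misoprostol, the protocol's Background says "It also induces uterine contractions".

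SAP 6.2.2 makes the ITT set, all randomised women, the primary population for efficacy. No section says how women without an oxytocin start enter this endpoint.

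**The concern.** The interval needs a start time, and a woman who delivers without oxytocin has none. She drops out of the comparison by definition, whatever population the SAP names. The set that remains is formed by a decision taken after treatment has begun. If the arms differ in who reaches oxytocin, and if women who do not need it would have laboured at a different speed, then the remaining groups differ in prognosis even when treatment does nothing to labour speed.

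The documents make unequal oxytocin use plausible. Misoprostol causes contractions, and women may go into labour before the 12-hour assessment.

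The other provisions do not repair this:

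- ITT cannot be met for a quantity that some randomised women do not have.
- LOCF (SAP 6.1.3) is meant for trends over time and cannot supply a missing clock start.
- The Kaplan-Meier display in SAP 7.3 is stated for delivery time. If it were extended to this interval, the clock would still start at oxytocin.

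At stake is a nominally significant p-value in an open-label trial that could be read as a treatment effect on labour after oxytocin.

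**Working it through.** The documents state no figure for this endpoint, so there is none to reproduce. The check asks how large a false difference could be under stated assumptions.

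**From the documents:** 322 women randomised 1:1 (Protocol, Study Design), so 322/2 = 161 per arm before exclusion; 5% level (SAP 6.1), taken as two-sided.

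**Assumed, because the documents are silent:** SD of labour time 6 h in both arms; the fraction f in each arm that skips oxytocin; the correlation ρ between early labour and later labour speed, from 0 to 0.5.

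**Model with no treatment effect.** Labour time is T = μ + 6[ρu + √(1−ρ²)e], with u and e independent standard normal and the same distribution in both arms. The fraction f with the lowest u (the earliest to labour) skip oxytocin. With z_f the normal quantile of f and φ the normal density:

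- Mean of u among recipients: λ = φ(z_f)/(1−f).
- False difference, Dilapan-S minus misoprostol: d = 6ρ(λ_D − λ_M).
- Variance among recipients: 36(1 − ρ²δ), with δ = λ(λ − z_f).
- SE: pooled over n = 161(1−f) per arm.
- Rejection: Φ(k − 1.96) + Φ(−k − 1.96), with k = |d|/SE.

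**Values of λ and δ:**

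- f = 5%: λ = 0.1031/0.95 = 0.109; δ = 0.190.
- f = 10%: λ = 0.1755/0.90 = 0.195; δ = 0.288.
- f = 30%: λ = 0.3477/0.70 = 0.497; δ = 0.507.

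**One case in full (10% v 30% skipping, ρ = 0.5):**

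- d = 6 × 0.5 × (0.195 − 0.497) = −0.91 h.
- Recipients: 161 × 0.90 = 144.9 and 161 × 0.70 = 112.7.
- Variances: 36(1 − 0.25 × 0.288) = 33.4 and 36(1 − 0.25 × 0.507) = 31.4; pooled 32.55.
- SE = √[32.55(1/144.9 + 1/112.7)] = 0.717.
- k = 0.905/0.717 = 1.263; rejection = 0.243 + 0.001 = 24%.

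| Skipping oxytocin, Dilapan-S v misoprostol | ρ | False difference (h) | Rejection |
|---|---|---|---|
| 10% v 10% | 0 to 0.5 | 0 | 5% |
| 10% v 30% | 0 | 0 | 5% |
| 5% v 10% | 0.3 | −0.16 | 5.6% |
| 5% v 10% | 0.5 | −0.26 | 6.7% |
| 10% v 30% | 0.3 | −0.54 | 11% |
| 10% v 30% | 0.5 | −0.91 | 24% |
| 30% v 10% | 0.3 to 0.5 | +0.54 to +0.91 | 11% to 24% |

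A negative sign means that Dilapan-S looks faster.

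**Second model, to see whether the distribution or the rank test matters.** Labour time was simulated as lognormal (assumed mean 14 h, SD 8 h), 161 per arm, 3,000 runs, with oxytocin use of 90% v 70% and ρ = 0.3 to 0.5. The false difference was −0.7 to −1.1 h. Rejection was 11% to 18% by t-test and 12% to 22% by Wilcoxon test, so the rank test does not help. A t-test on the same simulated labour times in all women, with or without oxytocin, rejected in about 5% of runs.

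**The case against.** The strongest reply is that both the direction and the size are open. A reader might infer that the fastest misoprostol women leave the comparison, so that Dilapan-S will look faster after oxytocin. The documents do not establish that:

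- Under Oxytocin administration, the protocol gives oxytocin for augmentation as well as induction. A woman already contracting on misoprostol can still receive it and stay in the comparison.
- The protocol's Background says that Dilapan-S also activates endogenous prostaglandins, and early spontaneous labour is provided for in both arms.
- Women can miss oxytocin for reasons other than fast labour. A persistent abnormal fetal heart tracing is a listed reason for early examination, and a caesarean could precede oxytocin.

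All of this stands. No direction can be claimed, and an honest range starts at zero.

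A second reply is that ripening-to-delivery time is already listed and already tested. That is true, and it makes the remedy smaller, but it does not make the oxytocin comparison valid.

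A third is that delivery time in SAP 3.2 may be a heading over both intervals, since the table list has a single analysis of delivery time, and that the phrase about tests being used as appropriate leaves discretion. Either reading is possible. Neither labels the oxytocin interval as a comparison within a selected subset, and the restriction to recipients follows from the definition even though the SAP does not write it down.

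Finally, this is one unpowered secondary endpoint to which the documents attach no decision. That stands and limits the importance of the point.

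**Conclusion.** The point holds as a minor one. Followed as written, the SAP tests an interval that exists only in a subset formed after randomisation, and such a test can reject too often when treatment has no effect on labour speed. Bias requires two conditions together: oxytocin use must differ by arm, and women who skip oxytocin must differ in labour speed from those who receive it. The first is plausible from the documents; neither is quantified there.

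The illustrated range, from no bias to just under an hour in either direction, rests wholly on the assumed SD, correlation and skipping rates. It shows what can happen and does not predict what this trial will show.

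A reader might also infer that the main efficacy conclusion is at risk. It is not: vaginal delivery within 36 hours is counted from the start of ripening and does not depend on receiving oxytocin.

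**What to change.** In SAP 7.3, exempt oxytocin-to-delivery time from the t-test and Wilcoxon test. Report it by arm as descriptive, in women who started oxytocin, beside the number and proportion in each arm who did so.

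Base any between-arm inference on time to delivery on the already listed interval from the start of cervical ripening, by randomised arm. State two things that the SAP leaves open for it: the clock start for randomised women who never start ripening (for example, randomisation), and how caesarean deliveries are handled in the comparison, since the SAP mentions them only as censoring in the Kaplan-Meier display.

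The cost is a short addition to the SAP and the loss of one p-value. Trial conduct does not change.
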